2.4 Rationale and definition of cohort

Endometrial cancer has well-defined risk cohorts. Epidemiologic studies have consistently shown that women who are overweight are at increased risk of endometrial cancer, and women who are very overweight are at very increased risk. Brinton et al conducted a large case control study and found that women who were greater than 200 lbs. had a relative risk of 7.2 compared with women less than 125 lbs.[41] In order to maximize risk for our cohort, we will include women who fulfill standard criteria for obesity grade I and above, which is defined as body mass index (BMI) greater than or equal to 30 kg/m². An upper age limit of 65 has been set. We chose not to include pre-menopausal women in this study because of the confounding problem of irregular cycling and varying estrogen levels in pre- menopausal obese, insulin resistant women (i.e. women with polycystic ovary

syndrome). We also chose not to include women who fulfill criteria for diabetes, since additional agents, other than metformin, may be necessary to control their diabetes.

2.5 Safety issues of metformin, as chemoprevention for endometrial cancer in a cohort of obese women

Metformin hydrochloride (*Glucophage, Bristol-Myers Squibb*) is a biguanide antihyperglycemic agent. It corrects Type II diabetes mellitus by altering glucose production and absorption, in contrast to sulfonylureas, which stimulate insulin secretion. Specifically, metformin improves insulin sensitivity by increasing peripheral glucose and utilization, decreasing intestinal absorption of glucose and suppressing glucose production by the liver, thus lowering serum insulin levels.

We believe that metformin is not only safe in this population, but also beneficial.

2.5.1 A randomized phase III study with metformin was conducted in this same population i.e.: insulin resistant but non-diabetic patients (the Diabetes Prevention Program Randomized Trial NEJM 2002 (6)346, p393), and demonstrated that metformin was well tolerated in a population of insulin resistant, non-diabetic individuals (and decreased the incidence of diabetes).[42] This study demonstrates the safety of using this drug in this population and also suggests that we can potentially dovetail the cardiovascular and metabolic health benefit of the drug with chemoprevention.

2.5.2 Metformin does not increase secretion of insulin and therefore does not cause hypoglycemia.

2.5.3 Use of metformin in insulin resistant but non-Type II diabetics also has precedence in the treatment of women with polycystic ovarian syndrome, or PCOS. Clinicians use metformin or thiazolidinediones, insulin-sensitizing agents, in young PCOS women, whose underlying metabolic problem is insulin-resistance. Interesting, treatment for their insulin resistance results in normalization of their pituitary/reproductive hormone axis and subsequently results in ovulation and regular periods.[43, 44]

2.6 Biomarkers as surrogate endpoints

Endpoints for chemoprevention studies can either be development of cancer, or a surrogate for the development of cancer. In this study we will use surrogate biomarkers as the primary endpoint.

Identification of appropriate biomarkers is essential for this study. An ideal biomarker is a histological or molecular "red flag" that precedes the onset of cancer. Ideal surrogate endpoint biomarkers are quantitative and are modulated by

chemopreventive agents.[45] In our prior endometrial cancer chemoprevention study of women with HNPCC, we evaluated a panel of 30 biomarkers thought to be relevant in endometrial carcinogenesis. From that study, we have narrowed down the field to a subset of 6 validated, estrogen-regulated genes and a proliferation marker Ki-67.[46]

The following is a summary of the analyses to be performed on the endometrial biopsies at baseline and following four months of hormonal therapy:

- **Proliferation index Ki-67**
- **Histology**
- **Quantitative PCR transcript analysis**

Table 1: Estrogen-dependent panel of genes for PCR transcript analysis

Gene	Marker / Pathway
Proliferating Cell Nuclear Antigen (PCNA)	Proliferation marker
Insulin-like Growth Factor Receptor (IGF-IR)	IGF Pathway
Retinaldehyde dehydrogenase 2 (RALDH2)	Retinoid Pathway
Secreted Frizzled-Related Protein 4 (sFRP4)	Wnt Pathway
Survivin	Apoptosis
Estrogen-induced gene (EIG121)	Novel gene of unknown function

Biomarkers associated with metformin function and downstream signaling includes:

- phospho-AMPKa
- phospho-ACC
- phospho-mTOR
- phospho-S6 ribosomal protein.

We will examine pre- and post- treatment endometrial biopsies for histology and proliferation using Ki-67. These are standard surrogate endpoints used in cancer chemoprevention trials. In addition, our group has identified a set, or panel of genes expression assays relevant to estrogen-dependent endometrial proliferation, hyperplasia and cancer. The set of genes, listed in Table 1 above will also be examined using real-time PCR in the pre- and post- treatment biopsies.

The Ki-67 as well as the biomarkers associated with metformin action analysis will be performed by the MD Anderson Core Histology lab and read by [name] in the Pathology Core. Q-PCR analyses will be performed by [name], PI of the Biomarkers core. [name] has been interested in identifying genes in human endometrium whose expression is altered by hormone replacement therapy (HRT). Over the last 5 years he has used several techniques including differential display, microchip array screening, and real-time quantitative PCR to find such genes. The tools he has developed are directly applicable to the investigation of surrogate endpoint biomarkers (SEBs) in HNPCC patients treated with estrogens or estrogens plus

progestins.

2.7 Description of Proposed Involvement of Human Subjects

This study will be conducted at UT-MD Anderson Cancer Center, with recruitment focused on 100 subjects. Women $>= 50$ to $<= 65$ years old, with $\text{BMI} \geq 30 \text{ kg/m}^2$, fasting blood glucose $\leq 126 \text{ mg/dL}$, and hyperinsulinemia, but not frankly diabetic are eligible. Those women who demonstrate fasting blood glucose greater than 126 mg/dL will not be referred for the study, and will instead be referred to contact an Endocrinologist from their insurance provider for management of diabetes. Women of any race or ethnicity who meet the eligibility criteria will be enrolled in the study. Based on our participant base, we anticipate the minority inclusion to be: 58% White and Non-Hispanic; 30% Hispanic; and 12% African-American.

Hyperinsulinemia will be determined by using the fasting insulin and fasting glucose levels to calculate the QUICK I, an index of insulin resistance. $\text{QUICK I} = 1 / [\log \text{ fasting insulin } (\mu\text{U/ml}) + \log \text{ fasting glucose } (\text{mg/dL})]$. Values below and equal to 0.357 will be used to identify women who are insulin resistant. [47-49].

3.0 Background Drug Information

Metformin hydrochloride is a biguanide antihyperglycemic agent. It corrects Type II diabetes mellitus by correcting insulin resistance, in contrast to sulfonylureas, which stimulate insulin secretion. Specifically, metformin improves insulin sensitivity by increasing peripheral glucose and utilization, decreases intestinal absorption of glucose and suppress glucose production by the liver. Metformin does not increase secretion of insulin and therefore does not cause hypoglycemia. In both animal models and in humans, metformin decreases plasma glucose.

3.1 Agent

Metformin hydrochloride (Greenpark Pharmacy)

3.2 How supplied

Each capsule contains 425 mg of metformin hydrochloride that will be used in this study.

3.3 Dose groups

Metformin hydrochloride 425 mg capsule(s) vs. no treatment. See below for monthly dose and duration of Metformin hydrochloride.

3.4 Dose and Duration of exposure

Table 2: Monthly Dosage of Metformin or Placebo capsule(s)

	Week 1	Week 2	Week 3	Week 4
1 st Month	One capsule daily	One capsule 2X daily	One capsule 3X daily	Two capsules 2X daily
2-4 Month	Two capsules 2X daily	Two capsules 2X daily	Two capsules 2X daily	Two capsules 2X daily

- Orally for 120 days (plus or minus 10 days).
- The dose of metformin hydrochloride will be in 425 mg capsule(s) by mouth, the dose used in The Diabetes Prevention Program Randomized Trials.[50]

3.5 Half life

Following oral administration, approximately 90% of the absorbed drug is eliminated via the renal route within the first 24 hours, with a plasma elimination half-life of approximately 6.2 hours. In blood, the elimination half-life is approximately 17.6 hours, suggesting that the erythrocyte mass may be a compartment of distribution.

3.6 Administration

Metformin hydrochloride is self-administered.

3.7 Side effects

Diarrhea
Nausea/ Vomiting
Flatulence
Abdominal discomfort
Asthenia Ingestion
Weight gain Edema
Headache Heart
failure Lactic
Acidosis

3.8 Contraindications

3.9.1 Renal disease or renal dysfunction (e.g., as suggested by serum creatinine levels \geq 1.4 mg/dL [females] or abnormal creatinine clearance) which may also result from conditions such as cardiovascular collapse (shock), acute myocardial infarction, and septicemia.

3.9.2 Congestive heart failure requiring pharmacologic treatment.

3.9.3 Known hypersensitivity to Metformin hydrochloride.

3.9.4 Acute or chronic metabolic acidosis, including diabetic ketoacidosis, with or without coma. Diabetic ketoacidosis should be treated with insulin. This will be assessed based on symptoms reported and reviewed with research staff during monthly toxicity screening visits.

3.9.5 Metformin will require a two day hold if given certain contrast medicines before X-rays, CT scans, MRI, and other procedures.

3.9 Use during pregnancy

Studies have shown that the drug does not exert teratogenic or embryocidal effects on animals, but there are no controlled studies in women.

3.10 Manufacturer and Supplier

Greenpark Pharmacy

4.0 Participant Eligibility

4.1 Inclusion Criteria

4.1.1 For this study, only women will be enrolled

4.1.2 Body Mass Index (BMI) $\geq 30 \text{ kg/m}^2$

4.1.3 Not frankly diabetic, as measured by a fasting blood glucose $\leq 126 \text{ mg/dL}$.

4.1.4 Demonstrate hyperinsulinemia with a QUICK I value $</= 0.357$.

4.1.5 Age $>/= 50$ and $</= 65$

4.1.6 Zubrod Performance Scale 0-1

4.1.7 Hemoglobin $>/= 10 \text{ g/dL}$

4.1.8 TSH 0.27 – 4.20 $\mu\text{IU/mL}$

4.1.9 Menopause as defined as no menses for 1 year and / or FSH $\geq 25.8 \text{ mIU/ml}$.

4.1.10 Must be able to read, write, and speak English.

4.1.11 Must have a Primary Care Provider (PCP).

4.2 Exclusion Criteria

4.2.1 Prior hysterectomy or endometrial ablation.

4.2.2 ALT $\geq 2.0 \times$ Upper Limit of Normal (ULN)

4.2.3 Serum creatinine $\geq 1.4 \text{ mg/dL}$

- 4.2.4 Triglycerides (fasting) ≥ 400
- 4.2.5 Known inability to participate in the ongoing appointments for the four months of the study and scheduled follow-up tests.
- 4.2.6 Significant medical or psychiatric history which would make the participant a poor protocol candidate, in the opinion of the principal investigator, for any aspect of study participation including metformin, unsupervised exercise program or dietary behavior change.
- 4.2.7 Participant reported history of congestive heart failure
- 4.2.8 Prior treatment with Metformin
- 4.2.9 Currently being treated for diabetes or meeting criteria for new diagnosis of diabetes.
- 4.2.10 Known allergy to Metformin or other biguanide (Proguanil).
- 4.2.11 Use of Aromatase Inhibitors, GNRH-agonists i.e. Lupron, Zoladex within the last 6 months
- 4.2.12 Use of SERMS (selective estrogen receptor modulators) in the past 6 months, including Tamoxifen and Raloxifen
- 4.2.13 Hormone replacement therapy within the last 6 months
- 4.2.14 Women who have been treated with chemotherapy for prior malignant disease or currently have an untreated malignancy other than non-melanoma skin cancer
- 4.2.15 Participants who have had prior radiation to the pelvis

5.0 Design and Methods

5.1 Study Design

For the proposed study, post- menopausal women with a $BMI \geq 30 \text{ kg/m}^2$ who demonstrate insulin resistance will be recruited from the Harris Health Hospital (Lyndon B. Johnson General Hospital - LBJ), community, and from the employee pool at MD Anderson Cancer Center using various outlets as advertisement. Project LEAP fliers will be posted at the LBJ for recruitment purposes only. All consenting, study visits, and study procedures will be done at the MD Anderson Cancer Center.

Participants will be assessed for their eligibility, first during a **Screening Call**, in which interested women will call the contact number and be screened using the **Screening Script**.

- Screening Call
 - Participants are screened using screening script. Once preliminary eligibility has been determined, then their information is forwarded to the study research nurse.
 - Study research nurse will:
 - Obtain reported medical history and medication history and schedule for Screening Visit 1.

- Explain the informed consent process. Participant may review the informed consent information electronically by email, by telephone, or in-person.
- Instruct participant on fasting and explain the blood tests to be collected on Visit 1 (See Table 5: Study Parameters for the list of lab tests to be collected on Screening Visit 1.)
- Provide driving directions to MD Anderson Cancer Center.
- Answer any relevant questions or concerns of the study.
- Initiate a New Patient (participant) Intake form by phone and send to Mays Clinic Gynecologic Oncology Business Center. Instruct participant that she will register in-person at the Mays Clinic Gynecologic Oncology Business Center on Screening Visit 1 day to obtain Medical Record Number (MRN).

5.2 Screening Visit 1

- Screening Visit 1 includes:
 - a. Registration at Mays Clinic Gynecologic Oncology Business Center (MCGOBC) to obtain a Medical Record Number (MRN).
 - b. Confirm that participant has fasted that day. Review previous information discussed by phone, and answer questions as needed.
 - c. Participant to meet with study Gynecologist briefly at MCGOBC for obtaining consent and discussing any concerns of the study. Once consent is attained then participant will be scheduled for laboratory tests to be collected during the same day (see Table 5: Study Parameters for the list of laboratory test to be collected for Screening Visit 1).
 - d. Pre-registration completed in CORe (See section 5.6 for Registration Process).
 - e. Provide participant education:
 - i. Endometrial biopsy (education packet that lists pre- and post- procedure instructions and contact information). See Appendix L for Patient Education Packet on Endometrial Biopsy (EMB).
 - ii. Taking NSAIDs (Non-Steroidal Anti-inflammatory Drugs) orally such as ibuprofen or Motrin or Advil if no prior allergies and available over the counter.
 1. Pre-biopsy: 600 mg of NSAIDs once approximately 1 hour before EMB.
 2. Post-biopsy: 600 mg of NSAIDs every 6 hours as needed for cramps or pain.

- iii. Participants who are unable to take ibuprofen / Motrin / Advil and have no allergies can also take acetaminophen (Tylenol) over the counter as an alternative NSAID.
 - 1. Pre-biopsy: 325 mg acetaminophen take once approximately 1 hour before EMB
 - 2. Post-biopsy: 325 mg of acetaminophen every 6 hours as needed for cramps or pain

At the Screening Visit 1, participants will be asked to complete one 24-hour dietary recall during the screening visit, using NCI's online ASA-24 system. Anytime between the Screening Visit 2 and 7 days post biopsy, the participant will complete two additional 24-hour dietary recalls (one on a weekday and 1 on a weekend). These additional recalls can be completed by phone or using their own home computer. Participants will also be given the survey packet to be completed before they return for the Screening Visit 2. Both the 24-hour diet recall and survey packet are described in detail below. All participants will be given an accelerometer (to obtain objective measure of physical activity), shown how to use it, and asked to wear it for one week between the screening visit and

7 days post-biopsy. They will return the accelerometer at the Screening Visit 2. If they are not able to return it at the second visit, they may return it by mail (prepaid mailer will be provided) or at their first intervention session (if randomized to receive the lifestyle intervention).

5.2.1 24-hour Dietary Recall

The Automated Self-administered 24-hour Dietary Recall (ASA24) will be used to document the participant's food intake for a total of 24 hours. Three recalls will be obtained at baseline and at 4 months, at least one of which will be for a weekend day. The overview of this questionnaire can be located at <http://riskfactor.cancer.gov/tools/instruments/asa24>. The participants will be given a designated url which will provide them access to the online questionnaire. If the participant does not have computer or internet access, the recall will be performed over the phone with the assistance of the Research Coordinator or Research Dietitian. To assist participants, the ASA24 utilizes graphics, pictures (to help approximate portion size), an animated guide, and audio cues and languages, which aid populations with low literacy [60]. The foods selected by the participants are from the USDA's Food and Nutrient Database for Dietary Studies' (FNDDS) most up-to-date database. Participants will begin completing these assessments approximately one week before their Screening Visit 2 and at four-month BRTC visits, with the third assessment completed within 1 week of the second visit/4-month visits.

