5.3.2 Anthropometric assessments

BRTC staff will measure the participants' height, weight, and waist circumference at baseline and 4th month. Height will be measured by having the participant stand evenly without shoes on a flat surface at a right angle to the movable vertical board or cap that is pulled down to lightly touch the most superior point of the head. Weight will be measured using either a standard beam scale or an electronic digital scale. The scale should be on a level floor, and participants should be gowned or wearing light clothing and no shoes. Waist circumference will be measured with the participant standing relaxed with hands hanging at her sides on the exhale. The tension-controlled measurement tape will be placed directly on the skin, horizontally around the narrowest part of the torso. If unable to locate the narrowest part of the waist, the participant will be measured 2-3 inches above the navel. The hip circumference will be measured with the participant standing relaxed with hands hanging at her sides on the exhale. The tension-controlled measurement tape will be placed directly on the skin or over the underwear, horizontally around the widest part of the hip/buttocks area.

The participant will undergo a whole body DEXA to measure body composition. The DEXA, routinely used to determine bone mineral density, has gained support in research application for assessing fat and lean body mass in whole body and in specific body regions [23, 24, 25]. Data from each scan will be as follows: percent body fat and % lean tissue, fat and lean mass for total body region as well as defined body zones (trunk, leg, and arms) expressed in grams.

5.4 Randomization / Visit 3

Participants, who are eligible based on results of the biopsy from Visit 2, will be called to schedule their third visit for randomization.

This study will use a 2 x 2 randomized design with all 100 subjects being randomized: 25 will receive both lifestyle intervention and metformin, 25 will receive the lifestyle intervention plus metformin placebo, 25 will receive metformin only, and 25 will receive metformin placebo but no lifestyle intervention. The participants randomized to the lifestyle change portion of the study will also have their first intervention session schedule for the same day as well. Treatments will last 4 months.

At Randomization / Visit 3, the participant will be:

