13.0 Schedule of Events

Table 5: Study Parameters (see next page)

Study Parameters	TAT ^a	Tube Top	Screening	Screening	Randomization	1 st Month	2 nd Month	3 rd Month	4 th Month	1 yr.
		Color	Visit 1	Visit 2	Visit 3	^b	^b	^b	^b	Follow-Up
Informed Consent			X							
History				X						
Physical				X		X				
Research Red Tube ^c		Red	X						X	X
Research Lavender Tube ^c		Lavender	X						X	X
Insulin (fasting)	4 days	Red	X						X	X
Glucose (fasting)	4 hrs	Mint	X						X	X
FSH (Spec Chem Test)	24 hrs	Gold	X						X	X
Hemoglobin	4 hrs	Lavender	X						X	X
Estradiol	5 days	Red		X					X	X
Estrone	5 days	Red		X					X	X
Testosterone (Chem Test)	24 hrs	Gold		X					X	X
DHEA-S	5 days	Red		X					X	X
Sex Hormone Binding Globulin (SHBG)	5 days	Red		X					X	X
Adiponectin	7 days	Red		X					X	X
A1C (Spec Chem Test)	24 hrs	Lavender	X						X	X
IGF-1	7 days	Red		X					X	X
Serum Creatinine	4 hrs	Mint	X			X			X	X
ALT	4 hrs	Mint	X			X	f	f	X	X
Triglycerides (fasting)	4 hrs	Mint	X						X	X
TSH	24 hrs	Gold	X						X	X
Dispense Medication & Pill					X	X	X	X		
Pill Count						X	X	X	X	
Pre-treatment EMB	72 hrs			X						
Toxicity and Compliance Assessment: Phone ^e						X	X	X	X	
Toxicity Assessment: In-person						X	X	X	X	
Post-treatment EMB	72 hrs								X	
DEXA				X					X	X
waist circumference				X					X	X
hip circumference				X					X	X
BMI				X					X	
ASA-24 (3) ^d			X						X	
Accelerometer			X						X	
Survey Packet				X					X	X

a) Turn Around Time

b) Plus or minus 10 days.

c) Research blood for future biomarker analysis.

d) 1 ASA-24 completed at Screening Assessment. Other 2 ASA-24s complete randomly between screening assessment and 7 days post-biopsy.

e) As needed

f) Only if ALT levels elevated as listed in CTCAE version 4.0.

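### Some baseline diet and accelerometer data could be collected after randomisation and the first lifestyle session, because nothing requires them to be finished first

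*Combined protocol and SAP*

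**What the plan says.** **Recalls.** Section 5.2 places the first baseline recall at Screening Visit 1. The other two, one for a weekday and one for a weekend day, may be done "Anytime between the Screening Visit 2 and 7 days post biopsy". Footnote d of Table 5 keeps the same end date but starts earlier: "Other 2 ASA-24s complete randomly between screening assessment and 7 days post-biopsy". Section 5.2.1 differs again: "Participants will begin completing these assessments approximately one week before their Screening Visit 2", with the third recall within one week of that visit.

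**Accelerometer.** Section 5.2 asks for one week of wear, ending no later than 7 days after the biopsy. The default for return is stated plainly: "They will return the accelerometer at the Screening Visit 2". A woman who cannot do that may mail the device back or, in the lifestyle arms, hand it in "at their first intervention session (if randomized to receive the lifestyle intervention".

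**Randomisation.** The baseline biopsy is done at Screening Visit 2 (section 5.3.1), and Table 5 gives it a 72-hour turnaround. Under section 5.4, women eligible on the biopsy result are called to schedule Visit 3. Those allocated to lifestyle "will also have their first intervention session schedule for the same day as well". No minimum gap between Visits 2 and 3 is given. Section 5.6 makes randomisation conditional on eligibility, laboratory tests and the biopsy; it does not mention the recalls or the accelerometer.

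**The concern.** A baseline value should describe the woman before she knows her allocation and before any intervention begins. Lifestyle allocation is open (section 9.0), and women in the no-lifestyle arms are asked to keep their current habits (section 6.1.4). Diet or activity recorded as baseline after Visit 3 can therefore differ systematically by arm. If lifestyle women have begun to change, their baseline already holds part of the effect, and their change to month 4 is measured as smaller than it was.

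Changes in diet and physical activity are secondary endpoints (section 1.2.2.2). Section 9.0 also names them as candidate mediators if lifestyle is found to affect Ki-67 or another outcome. An understated change in a mediator would weaken that analysis too. The plan has no rule for dating, flagging or excluding late baseline data, and a missed baseline cannot be collected again.

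**Working it through.** The plan states no figure on this point, so there is none to reproduce. The check is a timeline, then a simple dilution calculation.

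**Inputs from the documents**
- Day 0 is Screening Visit 2, the biopsy visit (section 5.3.1).
- The baseline window closes on day 7, or 168 h (section 5.2; Table 5, footnote d).
- The biopsy result is due at 72 h, or day 3 (Table 5).
- Randomisation and the first lifestyle session fall on the same day, Visit 3 (section 5.4).
- There are three baseline recalls, the first at Visit 1 (section 5.2).

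**Step 1: overlap.** Days of baseline window left after Visit 3 = max(0, 7 − day of Visit 3). At the stated turnaround, 168 − 72 = 96 h, or 4 days.

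| Day of Visit 3 | Days of window left |
|---|---|
| 3 | 4 |
| 4 | 3 |
| 5 | 2 |
| 6 | 1 |
| 7 or later | 0 |

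**Step 2: how many recalls can be late.** Under section 5.2 and Table 5, at most 2 of 3. Under section 5.2.1, which starts the recalls about a week before Visit 2, only the third, so 1 of 3.

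The weekend requirement in section 5.2 makes overlap plausible. Take a Monday biopsy (day 0) and Visit 3 on Thursday or Friday (day 3 or 4). The only weekend inside the window is then days 5 and 6, after Visit 3. The exception is a recall taken on the Monday itself and counted for the Sunday before.

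**Step 3: how many wear days can be late.** This depends on how the device comes back:
- Returned at Visit 2: none.
- Handed in at the first session: none after that session.
- Worn from the biopsy day and mailed back, with Visit 3 on day 3: up to 4 of about 7.

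**Step 4: dilution of dietary change.** Let D be the true change to month 4, k the number of late baseline recalls, and f the share of D already present when they are taken. With three equally weighted recalls, the baseline mean is shifted by (k/3) × f × D. Measured change is therefore D × (1 − k × f/3), an understatement of k × f/3. The documents give no value for f; I assume 0.10 to 0.50.

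| f | k = 1 | k = 2 |
|---|---|---|
| 0.10 | 0.10/3 = 3% | 0.20/3 = 7% |
| 0.25 | 0.25/3 = 8% | 0.50/3 = 17% |
| 0.50 | 0.50/3 = 17% | 1.00/3 = 33% |

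These figures apply to a woman with k late recalls. The effect on an arm mean is that figure times the proportion of women affected, which the documents do not allow one to estimate.

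**Step 5: what lies outside the problem.** The Ki-67 biopsy, DEXA and anthropometry are taken at Visit 2. The Godin questionnaire, which supplies the exercise factor for minimisation, is completed before Visit 2 (section 7.0). Recall 1 is at Visit 1. All precede randomisation.

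**The case against.** **Day 3 is the earliest date, not the expected one.** The result takes 72 hours, and the woman is then telephoned to arrange Visit 3. Section 5.6 also asks that all laboratory tests be completed. Table 5 lists Visit 2 assays with turnarounds of 5 days (estradiol, estrone, DHEA-S, SHBG) and 7 days (adiponectin, IGF-1). If completed means reported, Visit 3 falls at about day 7 and the overlap disappears. This is a fair reading but not a safeguard: those assays are not eligibility criteria in section 4.0, and section 5.4 ties Visit 3 to the biopsy result. It does mean that overlap is possible rather than certain.

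**A reader might infer from the return clause that the plan foresees baseline wear after the first session.** It does not show that. A device handed in at that session was worn before it. Nor is the clause a true contradiction of return at Visit 2: one is the default and the other its stated exception. What remains is that permitted wear runs past the default return date.

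**A reader might also infer a severe loss of signal.** If 4 of 7 wear days already showed the whole lifestyle effect, measured change would be 1 − 4/7 = 43% of the true change; with 2 of 7 days, 1 − 2/7 = 71%. Both need the full effect at once. The 43% case also needs wear from the biopsy day, return by mail and Visit 3 at exactly 72 hours. The programme described in section 6.2 does not support an immediate full effect: it has 16 weekly sessions, opens with an introductory one, and reaches its main activity topic at session 4.

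**A recall describes the preceding 24 hours.** One taken on the day of Visit 3 mainly reports intake before the session. That stands, and it narrows the exposure slightly.

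**Conclusion.** The point holds as a gap in scheduling rules. Following the plan as written, some baseline ASA-24 and accelerometer data could be gathered after open allocation and after the first lifestyle session. The exposure is 4 to 1 days if Visit 3 falls on days 3 to 6, and nil from day 7; the actual gap between Visits 2 and 3 is not stated. The likely direction is understated change in the lifestyle arms. The dietary range of 3-17% with one late recall and 7-33% with two rests wholly on the assumed 10-50% early change. I put no percentage on the accelerometer.

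It would be tempting to say that baseline diet and activity as a whole are contaminated. The documents do not support that: one recall and the Godin measure always come first, and the default return of the accelerometer is at Visit 2. The consequence is confined to the ASA-24 and accelerometer secondary outcomes and to their part in a conditional mediation analysis. The primary Ki-67 analysis, its sample size, the minimisation, and the weight and body-composition mediators are untouched. This is an inexpensive improvement, not a threat to the trial's main result.

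**What to change.** 1. In section 5.6, add completion of all three baseline recalls and the accelerometer wear week to the conditions for randomisation at Visit 3.
2. Record the date of each recall and wear day relative to Visit 3, and state in section 9.0 that any day recorded after randomisation is excluded from baseline.
3. Reconcile sections 5.2 and 5.2.1 with footnote d of Table 5, so that the recalls and the wear week each have one start and one end, both before Visit 3.
4. Keep the option of handing the device back at the first session. Removing it would prevent no post-session wear and could lose devices or data.

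With the first change in force the overlap is 0 days whatever the date of Visit 3. The cost is wording and scheduling: Visit 3 may wait a few days for some women. Where the exclusion rule is needed, those women will have fewer baseline recalls, though under section 5.2 the Visit 1 recall always remains.
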